Dietary Intervention: The intervention group will be seen by the kidney disease dietician at all clinical visits for the first 3 months (weekly for month 1, every other week for months 2 and 3). During months 2 and 3, in the weeks that the patients are not in clinic, they will receive telephone calls from the dietician. Thus the intervention involves weekly assessment for the first 3 months (in person or over the telephone). After 3 months, the patient will not receive any further active dietary intervention from the dieticians unless the patient wishes to continue using the dieticians advice per clinic protocol. Patients will be given adequate explanation of their caloric goals and dietary constituents such as the proportion of carbohydrates, fats and proteins they should consume. A daily log of all dietary intake will be recorded using the MyFitnessPal (<https://www.myfitnesspal.com>) application or website (if no smartphone is available). The dietician will review weekly diet log, goals and reinforce dietary recommendations. If the patient desires, additional sessions with the dietician will be provided to help patient reach their dietary goals. All patients in the intervention arm will be actively encouraged to increase physical activity as tolerated with the intent of being able to perform 150 minutes of cardiovascular exercise per week.

Previous studies have suggested providing 30 Kcal/Kg early after transplantation to account for the high catabolic rate and weight loss immediately after transplantation, followed by 25 Kcal/Kg for the long term dietary maintenance (26). However, these studies likely provided a higher caloric intake than may be necessary as the majority of the weight loss early after transplantation is thought to be due “fluid-weight” loss from solute and post acute tubular necrosis related diuresis. For the intervention arm, the estimated daily caloric intake (assuming a sedentary lifestyle), necessary to maintain steady body weight will be calculated using the Mifflin St-Jeor equation (27). For the first 7 days, we aim to provide the recommended calories to account for the higher catabolic rate early after transplantation. By the end of the first week, a net reduction of 500 kcal/day will be done allow an estimated weight loss of about 1lbs/week. If the goal of 1 lbs/week is not achieved we will increase the net caloric deficit by another 250 kcal/day to achieve the goal.

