For this study, the goal of the dietary intervention is reduction of overall caloric intake. However, we intend to maintain an adequate proportion of carbohydrates, proteins and fats as has been recommended previously for the purpose of kidney transplant patients (26). On average fat will provide <30% of all caloric intake, carbohydrates will provide 50% of total calories and protein at 1.3-2.0 g/kg in the first 7 days (to account for catabolic effects of surgery), followed by 0.8-1.0 g/kg for the remainder of the intervention.

For patients randomized to standard of care arm, the dietician will meet and provide instructions per the current University of Michigan Transplant Center protocol.

Tests, Procedures and Follow up:

Measurement of Glomerular Volume

Only patients with post perfusion biopsies are consented. Per transplant center protocol, all patients will also get a 3 month allograft biopsy. Biopsies from post perfusion and 3 months will be used to obtain glomerular volume. Glomerular volume measurements will be made on biopsies with at least 8 glomeruli. With assumption that glomeruli are spherical, the radius (R) will be calculated as $R = r \times 4/\pi$ as described by Weibel (28). Glomerular tuft volume will then be given by $4/3\pi R^3$. Globally, sclerotic glomerular will be excluded from the analysis. 3 month protocol biopsies will also be stained with monoclonal antibodies against TLE4, DAPI and Ki67 to identify podocytes, all nucleated cells in the glomerulus and actively dividing cells, respectively. All counting of cells will be done manually by either [name] (PI) or [name] (Co-I).

Urine processing: Left over urine (ideally, at least 50 cc) will be collected at the time of 3 month biopsies. The Urine will be centrifuged at 4°C for 15 minutes at 4000 rpm (3200×g). Two 2-ml aliquots of the supernatant will be removed and stored at -20°C for protein, creatinine, and other measurements. The urine pellet will be treated as mentioned previously(6).The pellet will then be suspended in RLT/ β -mercaptoethanol buffer and then frozen at -80°C for assay.

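### The calorie step-up rule sets no minimum intake, so a small patient who is stepped up can be prescribed about half of estimated requirement

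*Combined protocol and SAP*

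**What the plan says.** The Dietary Intervention section of the protocol starts from a requirement: "the estimated daily caloric intake (assuming a sedentary lifestyle), necessary to maintain steady body weight will be calculated using the Mifflin St-Jeor equation". Patients get full calories for the first 7 days. After that, "a net reduction of 500 kcal/day will be done allow an estimated weight loss of about 1lbs/week", and then: "If the goal of 1 lbs/week is not achieved we will increase the net caloric deficit by another 250 kcal/day to achieve the goal". As background, the same section cites earlier regimens of 30 kcal/kg soon after transplant, "followed by 25 Kcal/Kg for the long term dietary maintenance", and suggests these were probably more generous than needed.

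Clinic contact with the dietician is "weekly for month 1, every other week for months 2 and 3", with telephone calls in the other weeks. The dietician reviews the diet log weekly, and patients are encouraged to work up to 150 minutes of exercise a week. On composition: "On average fat will provide <30% of all caloric intake, carbohydrates will provide 50% of total calories", with protein at 0.8-1.0 g/kg after day 7.

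The Inclusion Criteria require a BMI of at least 25 and age 18-70; they give no minimum weight. The Exclusion Criteria remove bariatric surgery patients because of worry about malnutrition. Under Tests, Procedures and Follow up, prealbumin is measured at months 1 and 3 to look for malnutrition, with no threshold and no action. Safety Monitoring names hypoglycaemia as possible. Protection of Human Subjects describes the risk as minimal.

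**The concern.** A fixed deficit takes a larger share of the diet from a smaller person. Nothing in the rule stops the prescription at any level of intake, and nothing in eligibility keeps small patients out. Followed exactly, the text can put a small patient, within 3 months of transplant surgery and on triple immunosuppression, on about half of estimated requirement. That fits poorly with a trial presented as modest restriction at minimal risk. The protocol itself treats under-nutrition as a hazard, through the bariatric exclusion and the prealbumin tests, but attaches no action to either prealbumin result.

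The trigger makes this easier to reach. The weight loss that must be met to avoid a step is the same loss that the first deficit is expected to produce. A patient doing what was asked therefore sits on the threshold, not safely beyond it. The text also does not say whether loss is judged since the last visit or since the start.

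**Working it through.** **Inputs from the protocol.** Deficits of 500 kcal/day, and 750 kcal/day after one step; 1 lb/week; 25 kcal/kg; BMI of at least 25; age 18-70; protein 0.8-1.0 g/kg, carbohydrate 50%, fat under 30%.

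**Assumed, because the protocol does not print them.** Mifflin St-Jeor coefficients: 10 × kg + 6.25 × cm − 5 × age, then −161 for women or +5 for men. Sedentary factor 1.2, with 1.4 shown as a range. Protein at 4 kcal/g.

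**The protocol's own figure.** 500 × 7 = 3,500 kcal/week for about 1 lb, so the protocol implies 3,500 kcal per lb. At 750 kcal/day the expected loss is 750 × 7 / 3,500 = 1.5 lb/week. The trigger (under 1 lb/week) therefore equals the loss expected at the first deficit.

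**Intake left, at 25 kcal/kg.** Formula: 25 × weight − deficit, with the whole deficit taken from food. A weight of 60 kg is BMI 25 at 1.55 m (25 × 1.55² = 60.1).

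| Weight | Requirement | Left at −500 | Left at −750 |
|---|---|---|---|
| 60 kg | 1,500 | 1,000 (67%) | 750 (50%) |
| 75 kg | 1,875 | 1,375 (73%) | 1,125 (60%) |
| 100 kg | 2,500 | 2,000 (80%) | 1,750 (70%) |

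**Intake left by the protocol's own method.** Woman, 60 kg, 155 cm, after one step:

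| Age | Equation | × 1.2 | Left at −750 | Share at × 1.4 |
|---|---|---|---|---|
| 30 | 1,257.75 | 1,509 | 759 (50%) | 57% |
| 50 | 1,157.75 | 1,389 | 639 (46%) | 54% |
| 70 | 1,057.75 | 1,269 | 519 (41%) | 49% |

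A 60 kg, 155 cm man aged 50 keeps 838 of 1,588 (53%) at × 1.2. At age 50 and × 1.2, a 75 kg, 173 cm patient keeps 56% (woman) or 61% (man), and a 100 kg, 173 cm patient 63% or 66%. In general, anyone whose requirement is 1,500 kcal/day or less is left with half or less after one step.

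**Do the composition targets act as a minimum?** For 60 kg, protein is 48-60 g, or 192-240 kcal, which is 26-32% of 750 kcal. With 50% carbohydrate, 18-24% is left for fat, inside the limit. All three targets can be met at 750 kcal, so they do not stop the step.

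**The case against.** **The prescription is supervised.** There is weekly log review, weighing and examination at clinic visits, adverse-event reporting, and withdrawal at any time. A sensible dietician would probably not push a small patient to 519 kcal/day. That is true and lowers the practical risk, but none of these measures states a minimum or makes the step conditional on one.

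**Exercise can supply part of a net deficit.** The requirement is computed as sedentary, and the step raises the net deficit rather than the food cut. If activity supplied an assumed 100 kcal/day (50-150), the 60 kg patient's food intake after a step would be 850 kcal (800-900), or 57% (53-60%) of 1,500. This stands, and it is why the shares above are conditional on the deficit coming wholly from food. The net shortfall is still 750 kcal/day.

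**The lowest shares rest on assumed coefficients.** Also true: from the protocol's cited figure alone, the 60 kg result is 50%, and at × 1.4 two of the three example women keep more than half.

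**A reader might infer that most adherent patients would be stepped up.** The documents do not support that. Take a patient at exactly a 500 kcal/day deficit, a week-1 baseline and seven later clinic weights. Judge cumulative loss mechanically, with independent weighing errors and no fluid change. The patient avoids every miss only if the baseline error is the most favourable of eight, so the chance of at least one miss is 1 − 1/8 = 88%. But the protocol itself says "the majority of the weight loss early after transplantation is thought to be due" to fluid. With 1 kg of fluid lost by week 2 and a weighing SD of 0.5-1.0 kg (both assumed), simulation gives 29-61%; with 2 kg, 1-29%. With 100 kcal/day of activity and no fluid loss it gives 70-78%; with activity and 1 kg of fluid, 13-47%. The goal is also worded approximately, and a dietician reviews it. A range from 1% to 88% is not an estimate.

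**A reader might also infer repeated escalation, or a biased comparison.** The rule reads naturally as one added step, and the figures here use only one; the gap is that no cap is written. A stricter diet in some patients changes the treatment given, not the validity of comparing randomised arms.

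**Conclusion.** The concern holds in a limited form and should be dealt with. The rule prescribes a fixed deficit with no minimum intake, and eligibility has no minimum weight. After one step taken wholly from food, a 60 kg patient keeps 50% of requirement at 25 kcal/kg. A 60 kg, 155 cm woman keeps 41-50% across ages 30-70 at an assumed factor of 1.2, and 49-57% at 1.4. Two conditions must both be met: the patient is small, and has been stepped up. Before a step the 60 kg patient keeps 67% at 25 kcal/kg, and at 75-100 kg patients keep roughly 56-70% after one. With about 15 patients planned for the diet arm and no weight distribution given, the number affected is unknown and may be small.

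Patients who follow the diet can be stepped up, because the trigger is the loss they are expected to show. How often depends on fluid loss, activity and dietician judgement, and cannot be fixed from the documents. This is a matter of participant protection and of a clearly defined intervention; the randomised comparison is not affected.

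**What to change.** Amend the step-up rule in the Dietary Intervention section:

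- (a) Set a minimum prescribed intake, as a share of the Mifflin St-Jeor requirement or in kcal/day, with the value chosen by the investigators and dietician. Apply neither the 500 kcal reduction nor the 250 kcal step where it would take the prescription below that minimum.
- (b) State that there is one step only, with a maximum deficit of 750 kcal/day.
- (c) Before stepping, require that the diet log already reviewed each week shows intake on target; if it does not, reinforce adherence instead.
- (d) Return to maintenance intake on a low month-1 prealbumin or on hypoglycaemia, with thresholds stated. The month-1 value is the useful one, since the month-3 draw falls near the end of the intervention: "After 3 months, the patient will not receive any further active dietary intervention from the dieticians", unless the patient asks to continue.

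Report how many patients were stepped up and when.

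The cost is protocol text; the log, clinic weights, dietician contact and prealbumin are already planned. The downside is slightly less contrast between arms in the smallest patients.

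A tolerance on the weight goal, averaged over about 4 weeks, is optional and I would not require it. With 2-4 weeks assumed for fluid to settle, the first step would fall at week 6-8 of a 12-week intervention.

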Aim 1: Test the hypothesis that modest CIR (~500 kcal/day) reduces the glomerular growth rate associated with kidney transplantation. For this pilot study, we will randomize 15 overweight or obese patients ($BMI > 25 \text{ kg/m}^2$) patients to dietician guided modest CIR or standard of care. All patients will undergo standard protocol biopsy at time 0 and 3 months post-transplantation. We will compare the difference in glomerular volume, number of Ki67 positive (actively dividing) glomerular cells, DAPI positive (all glomerular cell nuclei) and TLE4 positive (podocyte nuclei) intraglomerular cells from at least 8 glomeruli/patient. In those patients in whom the CIR protocol reduced post-transplant weight gain we expect to see lower glomerular growth rate as demonstrated by reduced glomerular volume increase and a lower number of Ki67 positive intraglomerular cells. As podocytes don't divide we also expect to see a lower proportion of podocytes (TLE4 positive/total DAPI positive nuclei) reflecting the increased growth rate of non-podocyte cells in the glomerulus.

Aim 2: Test the hypothesis that modest CIR reduces podocyte hypertrophic stress as assessed by a reduction in the urinary podocyte detachment rate. For this aim we will collect urine samples at the time of 3-month protocol biopsies and compare the urinary podocin to creatinine ratio as well as markers of podocyte "hypertrophic stress" including the urine podocin to nephrin ratio across both groups (10). We expect a lower urinary podocyte detachment rate as well as lower urine podocin to nephrin ratio in the intervention arm.

These studies will provide insight into the feasibility of conducting larger clinical studies using CIR in the early post-transplant period. Further, they may provide insights into the mechanistic role of caloric restriction on post-transplant glomerular growth, as well as their impact on reducing post-transplant weight gain, post-transplant diabetes mellitus and hypertension, all of which alone or in combination can affect allograft and patient survival. With the average cost of dialysis at 100,000 USD/year, even a 1-year improvement in allograft longevity of the approximately 15,000 kidney transplants performed every year translates into cost savings of approximately 1.5 billion dollars.

BACKGROUND INFORMATION

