1. Yang et al. JASN 2015. Demonstrates that allograft recipients have a 6-fold increased rate of podocyte detachment and that post-transplantation kidney allografts have an increased glomerular volume and reduced podocyte density, and podocyte number per glomerulus decreases in association with development of transplant glomerulopathy(6).
2. Naik et al. JCI Insight 2016. Demonstrates that the podocyte depletion hypothesis can account for the unexpectedly short allograft half-life and the donor-age effect on allograft outcomes(7).
3. Nishizono et al. JASN, manuscript accepted for publication. Demonstrates in a rat model that CIR reduces glomerular enlargement, podocyte stress, podocyte reduction rate and glomerulosclerosis

By other investigators:

- Previous dietary intervention trials in clinical transplantation demonstrate feasibility in reducing weight gain post-transplant. A previous study compared patients who received weekly dietary advice to identical historical controls. At baseline both groups had identical weights. By 4 months post-transplant the intervention group had gained on average 2 kilograms compared to 7 kilograms in the historical control. By the end of the first year, the intervention arm had gained 6 kilograms compared to the 12 kilograms in individuals that received standard post-transplant dietary advice(11).

STUDY DESIGN AND METHODOLOGY

Prospective randomized single center clinical trial with un-blinded endpoint evaluation. The study is a pilot interventional trial comparing the impact of modest caloric intake reduction on glomerular growth and podocyte parameters after kidney transplantation. This pilot study plans to enroll 30 patients at the University of Michigan. We will follow patients for 12 months after their transplant.

Study Endpoints

Primary Endpoint for Aim 1: Assess differences in change of glomerular volume from immediate post perfusion biopsies to those obtained at 3 months between both arms. Further we will also investigate the

differences in number of Ki67 positive, DAPI positive (all glomerular cells), TLE4 positive (all podocytes) intraglomerular cells from at least 8 glomeruli/patient.

Primary Endpoint for Aim 2: Assess differences in urinary podocyte detachment rate (measured as urine podocin mRNA to creatinine ratio) as well as markers of podocyte “hypertrophic stress” such as urine podocin to nephrin ratio.

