Statistical considerations and analytical plan: Previous animal studies have shown that approximately 5 animals in each arm (dietary restriction vs. ad lib) has been sufficient. However, given lack of any previous data in humans and higher expected variability, we plan on recruiting 15 patients in each arm in this pilot trial. Further trials will use data obtained from this trial to determine the number of patients necessary to adequately power future studies. The unpaired "t" test will be used to compare differences in glomerular: volume, DAPI positive nuclei, Ki67 positive nuclei, TLE4 positive nuclei. Differences in means of proportions will be measured z test . A linear regression model will be utilized to quantify the relationship between the continuous variables. Best-fit curve estimation, including quadratic and cubic models, will be utilized, if necessary, to demonstrate nonlinear associations between two continuous variables.

Safety Monitoring:

Although we do not anticipate any adverse events due to caloric restriction, all adverse events including serious adverse events that could be related or possibly related will be reported. Reducing caloric intake may cause hypoglycemia in some individuals.

Potential Pitfalls: Patient may not follow instructions on diet leading to higher than desired caloric intake causing the study endpoints to be affected. However, this may offer further insight into study design feasibility and allow us to make appropriate changes for future studies.

As glomerular hypertrophy can also be driven by donor and recipient body size mismatch we have tried to minimize that possibility by using the average BMI groups for both donors and recipients (BMI:25-30 kg/m²). Other interventions that can affect glomerular hypertrophy including the use of ACEi/ARBs, mTORi which will be avoided in the first 3 months post transplant. Theoretically , the use of antiproliferative drugs used in transplantation may limit cell growth and thus we may not see the full benefit of reducing hypertrophy by dietary interventions. However, since the control and the intervention arms are on the same immunosuppressive agents, we believe that the effect of caloric restriction on glomerular growth would still be possible to observe.

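### Minor: a z test is planned for an unnamed proportion; if that is the podocyte fraction TLE4/DAPI at 15 patients per arm, the t test planned for its components should be used

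*Combined protocol and SAP*

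**What the plan says.** The section on statistical considerations assigns the unpaired t test to four histology measures: "test will be used to compare differences in glomerular: volume, DAPI positive nuclei, Ki67 positive nuclei, TLE4 positive nuclei". It then adds: "Differences in means of proportions will be measured z test". It does not say which proportion this is or how it is formed. The planned size is given in the same section: "we plan on recruiting 15 patients in each arm in this pilot trial".

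The only histology proportion in the document is TLE4-positive nuclei over all DAPI-positive nuclei. Aim 1 names it as an expected finding ("we also expect to see a lower proportion of podocytes (TLE4 positive/total DAPI positive nuclei"), and the Anticipated Result paragraph repeats it as the TLE4/DAPI ratio. Study Endpoints does not list it; that section lists the separate counts: "differences in number of Ki67 positive, DAPI positive (all glomerular cells), TLE4 positive (all podocytes) intraglomerular cells from at least 8 glomeruli/patient". The cell markers come from the later biopsy only: "3 month protocol biopsies will also be stained with monoclonal antibodies against TLE4, DAPI and Ki67".

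The plan also records patient-level yes/no events under Tests, Procedures and Follow up, such as post-transplant diabetes and rejection. It does not link the z test to those either.

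**The concern.** The sentence can be carried out in at least three ways: on the mean of per-patient proportions, on nuclei pooled within an arm, or on patient-level yes/no outcomes. The error rate differs between them.

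On the first reading, the normal reference treats an SD estimated from 30 patients as known. It also gives the ratio a different test from its own numerator and denominator, in the same patients and with no reason stated. On the second, nuclei from one patient would count as independent observations. At stake is a somewhat optimistic p-value for a supporting measure, and possibly a badly optimistic one if nuclei were pooled.

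**Working it through.** **Inputs**

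- Patients per arm: n = 15 (statistical section). 2 × 15 = 30 agrees with the total under Study Design and Methodology. Aim 1 mentions 15 patients without saying per arm; 15 per arm is used here.
- Alpha and sidedness: not stated. Two-sided 5% is assumed, so the normal critical value is 1.960.
- Evaluable patients: 15 per arm as planned; 12 and 10 per arm are assumptions.
- Glomeruli per patient: at least 8 (Aim 1 and Study Endpoints).
- Nuclei per glomerulus and intraclass correlation (ICC): not in the document.

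No alpha, power, effect size or SD accompanies the sample size, so there is no calculation of the plan's own to reproduce beyond 2 × 15 = 30.

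**Reading 1: mean of per-patient proportions.** The statistic is the difference in arm means divided by s√(2/n), where s is the pooled SD on 2n − 2 degrees of freedom. With no true difference and roughly normal patient values it follows t on 2n − 2 df. Using 1.960 gives a true size of 2·P(t > 1.960):

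| n per arm | df | t critical value | true size of z test |
|---|---|---|---|
| 15 | 28 | 2.048 | 6.0% |
| 12 (assumed) | 22 | 2.074 | 6.3% |
| 10 (assumed) | 18 | 2.101 | 6.6% |

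Moving to t at 15 per arm raises the critical value by 2.0484/1.960 − 1 = 4.5%.

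**Reading 2: pooled nuclei.** With M nuclei per patient, the binomial variance is too small by the design effect DEFF = 1 + (M − 1)·ICC, and the size is about 2·[1 − Φ(1.960/√DEFF)]. M is large, because at least 8 glomeruli are counted, so even a small positive ICC matters. The true figure cannot be computed from the document.

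Illustration only, with both inputs assumed: at 50 nuclei per glomerulus, M = 8 × 50 = 400. An ICC of 0.005, 0.01 or 0.02 gives DEFF 2.995, 4.99 or 8.98 and a size of about 26%, 38% or 51%. At ICC 0 the size is 5%.

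**Reading 3: patient-level yes/no outcomes.** All 16 × 16 = 256 possible pairs of event counts at 15 v 15 were enumerated for the pooled-variance z test. Its exact size is 0.5% at an event rate of 0.05, 2.5% at 0.10, 5.0% at 0.20 and 4.6% at 0.50. The maximum is 5.5%, near 0.28.

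**The case against.** The strongest reply is that this is close to a preference. The link to TLE4/DAPI is inferred, the ratio is not a listed endpoint, and a pilot with no stated alpha or power claim will not turn on 6.0% against 5%. All of that stands, and it is why the point is minor. It does not remove the point: a test is specified, its target is not, and a better-matched test is already in the same paragraph.

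A reader might go further and infer that glomeruli will be analysed as independent observations, since each patient contributes at least 8 and no unit of analysis is stated. The document does not support that:

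- The statistical section counts in subjects throughout, and the cell-count wording sets a minimum number of glomeruli per patient.
- The volume rule ("Glomerular volume measurements will be made on biopsies with at least 8 glomeruli") is an adequacy threshold for a biopsy.
- The change in volume implies a per-patient value, because the two biopsies sample different glomeruli.

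As a labelled illustration only, 8 glomeruli treated as independent give DEFF = 1 + 7·ICC. The size would then be about 9%, 13%, 21%, 27% and 36% at assumed ICCs of 0.05, 0.1, 0.2, 0.3 and 0.5. These figures describe an analysis the text does not propose.

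A reader might also infer that later trials would be undersized, because the plan says "Further trials will use data obtained from this trial to determine the number of patients necessary to adequately power future studies". That does not follow. A sample-size calculation takes an SD, and those trials are to be sized in patients. With 8 glomeruli, the variance of a patient mean is (1 + 7·ICC)/8 of the variance between single glomeruli. A glomerulus-level SD used as a patient-level SD would therefore make the later trial too large, by 8/DEFF (5.9 times at ICC 0.05, 1.8 times at ICC 0.5).

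**Conclusion.** The point holds as a minor correction to a stated method. If the z test is for the mean of per-patient TLE4/DAPI values, its size is 6.0% against an assumed two-sided 5% at 15 per arm, rising to 6.6% if 10 per arm are evaluable. If it were run on pooled nuclei, the inflation would be larger but cannot be quantified from the document. If it is confined to patient-level yes/no outcomes, no material harm follows.

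The conclusion rests on the inferred target, the assumed alpha and approximately normal patient-level values. The unit of analysis for the Ki67, DAPI and TLE4 counts needs only a clarifying statement, because the text already implies the patient.

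**What to change.** Replace the z-test sentence with:

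> *TLE4/DAPI is computed as one value per patient and compared between arms with the same unpaired t test as the other histology measures; a z or exact test is used only for patient-level yes/no outcomes.*

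For clarity, state in the same place that the patient is the unit for the volume and cell-count comparisons.

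This costs a line or two of text and needs no extra data. The critical value for TLE4/DAPI becomes about 4.5% larger (2.048 instead of 1.960), so the test is slightly more demanding.
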